3.3 Secondary Endpoints

3.3.1 Clinical Endpoints

Hospital mortality to day 90, and alive and home (prior level of care) at day 90, and 28 day mortality will be compared between treatment groups using Pearson's chi-square test.

Hospital length of stay and healthcare facility length of stay will be analyzed only in survivors to day 90. We will use survivor average causal effect (SACE) methods to estimate each outcome among participants that would have survived in both treatment and control groups⁴. The SACE methodology includes a model for predicting survival using baseline covariates. The covariates used will be sex, age, Charlson, SOFA, baseline 25OHD as measured by LCMS, and race/ethnicity (non-Hispanic white versus other).

Ventilator-free days to day 28 will be compared between treatment groups using a t-test.

3.3.2 Physiological Endpoints

Binary endpoints will be compared between treatment groups using Pearson's chi-square test.

Ordinal endpoints will be scored as 1,2,3, ... and compared between treatment groups using the CMH mean score test.

Continuous endpoints will be compared between treatment groups using a t-test with two exceptions. The highest creatinine and CV SOFA score will be analyzed controlling for baseline value using repeated measures ANOVA with a treatment by time interaction and shared intercept at time 0 (baseline). This model is equivalent to ANCOVA controlling for baseline but is able to make use of all available data.

3.3.3 Safety Endpoints

Calcium levels to day 14 will be compared daily between treatment groups using a t-test. Binary occurrence of hypercalcemia (as defined by the protocol) to day 14 will be compared between treatment groups using Pearson's chi-square test.

Kidney stones to day 90 will be compared between treatment groups using Pearson's chi-square test.

Falls and fall-related fractures to day 90 will be compared between treatment groups using Pearson's chi-square test.

EQ-5D-5L at day 90 (adjusted for baseline) will be analyzed only in survivors to day 90. We will use survivor average causal effect (SACE) methods to estimate the outcome among participants that would have survived in both treatment and control groups as described above.

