### 3.6.2.3 Safety Endpoints

10. **Calcium levels to day 14:** Because the half-life of 25OHD is approximately 2 weeks, we will record clinically available serum or ionized calcium levels through day 14 for all randomized participants. In addition, we will measure baseline and day 3 in the first 300 randomized participants in real time, either as part of routine clinical care or as a research procedure if not available. Day 3 is the when 25OHD levels peak in ICU patients given 540,000 IU of vitamin D. While no prior study of acute vitamin D repletion, using similar high doses as our trial, has observed clinically important hypercalcemia, we will confirm these findings in the VIOLET trial. Because little change in calcium levels is anticipated, access to individual-level calcium results will not unblind study staff. During the trial, the DSMB may seek additional subject measurements for safety assessment, though this is not anticipated.
11. **Kidney stones to day 90:** While an association between hypervitaminosis D and kidney stones has been suggested, the relationship with high dose vitamin D supplementation and kidney stones remains controversial. We will assess for incident kidney stones by chart

review at the end of the hospitalization and by self-report at the 90 day phone call for those discharged from the hospital prior to day 90.

12. **Fall-related fractures to day 90:** The association between acute vitamin D supplementation and falls/fractures remains unclear. Most data suggest that high dose vitamin D in healthy outpatients may improve muscle function, balance, and bone mineral density, and thus decrease fall-related fractures, but other data suggest that high dose vitamin D supplementation may actually increase the incidence of falls/fractures. Because of this uncertainty and limited data in hospitalized patients, we will assess for incident fall-related fractures by chart review at the end of the hospitalization and by self-report at the 90 day phone call for those discharged from the hospital prior to day 90.

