## APPENDICES

### A. Time-Events Schedule

Measurement/Event	0	1	2	3	4	5	6	7	8-14	HOSP D/C	90
Demographics, history and physical	X										
HCG (females)	X										
Screening 25OHD test	X										
Risk factors for ARDS and mortality	X										
Home meds (calcium and Vitamin D)	X										
Charlson Co-morbidity score	X										
SOFA	X										
LIPS	X										
Study drug administration	X										
ARDS Assessment	X	X	X	X	X	X	X	X			
Vasopressors (yes/no)	X	X	X	X	X	X	X	X			
Highest creatinine		A	A	A	A	A	A	A			
Serum albumin level	A	A	A	A	A	A	A	A	A		
On-study Vitamin D medication		X	X	X	X	X	X	X	X		
Calcium level (safety labs)†	X	A	A	X	A	A	A	A	A		
Ventilator status	X									X‡	
Plasma for IL-6 (first 300 randomized participants)	X			X							
Plasma for banking†	X			X							
Whole blood for DNA banking	X										
Plasma for 25OHD level†	X			X							
EQ-5D-5L	X										X
Length of stay (hospital and healthcare facility)										X	X
Assessment of kidney stones and fall related fractures										X	X
Vital status										X	X

X: required

A: if available

†: Baseline required for all randomized participants; Day 3 required for first 300 randomized participants only

‡: If patient discharged from hospital prior to day 28 with ventilator-assisted breathing, day 28 ventilator status should be obtained (e.g., phone call to LTAC)

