 - Worst AKI severity in first 7 days (no, mild, moderate, or severe AKI by KDIGO criteria²)
 - Highest creatinine in first 7 days
- Cardiovascular failure to day 7
 - New vasopressor use ever to day 7 (Y/N)
 - Highest CV SOFA score in first 7 days
- IL-6 to day 3

Safety

- Calcium to day 14
 - Daily comparison to day 14
 - Hypercalcemia ever during the first 14 days (Y/N)
- Kidney stones to day 90
- Falls to day 90
- Fall-related fractures to day 90
- EQ-5D-5L at day 90 (adjusted for baseline)

Figure. Time to Mortality to Day 90 (confirmed deficient cohort)

Figure. 90-day Mortality by Baseline Vitamin D Level for (screened deficient cohort)

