3.1 Statistical Methods for Main Manuscript

All analyses are intention to treat, that is, all randomized participants within each cohort (screened deficient, confirmed deficient) will be included in the analyses specified for each cohort. The confirmed deficient cohort is the primary efficacy cohort per the protocol.

All significance testing will be two-tailed at $\alpha = 0.05$ with no adjustment made for multiple comparisons³

With the exception of the primary outcome, analysis is based on all available data with no imputation of missing data.

The causal clinical effect of treatment on outcomes defined only in patients who are on study is complicated by potential case mix imbalance between the treatment groups due to differential recovery and mortality. However, the proposed statistical methods for these outcomes maintain the correct comparison-wise Type I error rate under the global null of no treatment effect whatsoever on any patient.

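### Calcium is compared by separate daily t-tests that ignore the baseline value required for everyone; a baseline-adjusted longitudinal model with two named contrasts would answer the question better

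*SAP*

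**What the plan says.** - **Test.** SAP 3.3.3: "Calcium levels to day 14 will be compared daily between treatment groups using a t-test". The contents list for the main results table in SAP section 3 repeats it as "Daily comparison to day 14". No baseline term is mentioned. The same subsection adds one chi-square test of any hypercalcemia to day 14.
- **Error rate and missing data.** SAP 3.1 sets two-tailed tests at 0.05 "with no adjustment made for multiple comparisons". Outside the primary outcome, "analysis is based on all available data with no imputation of missing data".
- **Source of the values.** Protocol 3.6.2.3: "we will record clinically available serum or ionized calcium levels through day 14 for all randomized participants". Protocol 6.3 limits this to in-hospital values. The footnote to the Appendix A schedule gives the mandated samples: "Baseline required for all randomized participants; Day 3 required for first 300 randomized participants only".
- **Caveat.** SAP 3.1 says that effects on outcomes defined only in patients still on study are "complicated by potential case mix imbalance between the treatment groups due to differential recovery and mortality". It then defends the methods only for comparison-wise type I error when the drug has no effect on anyone.
- **Another model in the same SAP.** SAP 3.3.2, the subsection just before, analyses highest creatinine and cardiovascular SOFA "using repeated measures ANOVA with a treatment by time interaction and shared intercept at time 0". It notes that this approach controls for baseline and can use all available data.

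**The concern.** Protocol 9.1 names hypercalcemia as the main risk of the intervention. Appendix C lists it among study outcomes exempt from adverse-event reporting unless the investigator judges it related or of uncertain relationship. The calcium analysis therefore carries much of the weight in detecting harm, and the protocol expects to confirm that calcium changes little.

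Against that aim, a daily t-test has three weaknesses:

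1. It discards a baseline value that is collected from everyone. Precision is lost at no saving, and a small sustained rise is tested least precisely on late days, when few patients remain.
2. It produces a string of unadjusted results with none named as the main one, so an isolated significant day, or the absence of one, is hard to interpret.
3. Each later day compares groups selected after randomization by discharge, death and the decision to order a sample. The trial's hypothesis is lower mortality. If that is true, the condition under which SAP 3.1 defends its methods no longer holds.

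**Working it through.** **Plan figure.** The documents give no SD, detectable difference or power for calcium, so there is no calcium figure to reproduce. Their only design calculation, 87.4% power, concerns 90-day mortality.

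**Inputs from the documents.** Fourteen post-dose days; two-tailed 0.05 per test; no adjustment; available cases only; day-0 calcium required for all; up to 0.80 × 3000 = 2400 participants in the confirmed deficient cohort.

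**Step 1: repeated testing.**
- Expected false positives: 14 × 0.05 = 0.70.
- Chance of at least one if days are independent: 1 − 0.95^14 = 0.51.
- Days are in fact correlated. Simulating correlated test statistics gives:

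| Assumed correlation between days | 0.3 | 0.5 | 0.7 | 0.9 |
|---|---|---|---|---|
| Same for all pairs of days | 44% | 35% | 25% | 14% |
| First-order autoregressive | 49% | 46% | 39% | 24% |

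A separate simulation of 2400 participants, with the observed share falling from 95% to 35%, gave 32% to 44%, inside this range.

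**Step 2: baseline adjustment.** If calcium on a given day correlates rho with baseline, adjustment multiplies the variance of the treatment contrast by 1 − rho².
- rho = 0.3: 0.91, a 9% reduction.
- rho = 0.5: 0.75, a 25% reduction.
- rho = 0.6: 0.64, a 36% reduction.

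The documents do not give rho; this range is assumed.

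**Step 3: selection.** Two illustrations, both resting on assumptions.

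*Illustration A.* Discharge is 8 points faster in one arm, and calcium correlates 0.3 to 0.5 with illness. The day-7 bias is −0.02 to −0.04 SD. If the observed share falls linearly from 95% on day 1 to 35% on day 14, day 7 has 95 − 60 × 6/13 = 67%, or about 800 per arm. The standard error is then √(2/800) = 0.05 SD, so the bias is below one standard error.

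*Illustration B.* 2400 participants, SD 0.8 mg/dL, correlation 0.5 between all days, 80% sampled on each day in hospital, and discharge depending on the last observed calcium. Sixty runs per scenario, with Monte Carlo error of up to about 6 points, √(0.25/60). The shared-baseline model was given the true covariance, which flatters it somewhat.

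| Scenario | Day | t-test estimate (mg/dL) | Model estimate | t-test rejects | Model rejects |
|---|---|---|---|---|---|
| No calcium effect; calcium predicts discharge only in the control arm | 3 | +0.083 | +0.002 | 45% | 2% |
| | 7 | +0.170 | +0.004 | 90% | 3% |
| | 14 | +0.294 | −0.006 | 98% | 3% |
| True effect +0.15; same discharge rule in both arms | 3 | +0.140 | +0.147 | 95% | 100% |
| | 7 | +0.131 | +0.147 | 72% | 93% |
| | 14 | +0.118 | +0.148 | 40% | 65% |

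The first scenario is a strong assumption, and exchanging the arms reverses its sign. With no calcium effect and the same discharge rule in both arms, neither method was biased: both were within 0.01 mg/dL on days 3, 7, 10 and 14.

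**Step 4: what the model does not do.** With no calcium effect and the same discharge rule, at least one of 14 daily contrasts was significant in 40% of runs for the t-tests and 48% for the model. Changing the model therefore leaves the multiplicity in place. The single average over days 1 to 14 rejected in 3% to 7% of runs without a calcium effect. Two named contrasts at 0.05 would give 1 − 0.95² = 9.75% if independent.

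**The case against.** **The plan does not rest on the daily tests alone.** The hypercalcemia chi-square is one test, aimed at the clinically important event rather than a small mean shift. Protocol 2.10, 7.1 and 9.5 also provide for a review of calcium in the first 300, with day-3 sampling required and the DSMB involved. This stands. A reader who inferred that the SAP offers only fourteen answers to the calcium question would be wrong. The chi-square, however, counts only those measured, and the first-300 review is an early safety check, not a final-report contrast.

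**The SAP is open about its choices.** It states that there is no multiplicity adjustment and concedes the case-mix problem. For a harm, leaving tests unadjusted favours detection and is defensible. This also stands, so the proposal keeps the daily estimates and asks for no alpha penalty.

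**The SAP 3.3.2 model is not ready-made for calcium.** It is written for the highest creatinine and cardiovascular SOFA over 7 days, and most naturally reads as a baseline-adjusted comparison of a per-patient worst value. Creatinine has no mandated post-baseline draw, whereas calcium has one on day 3 in the first 300. A 15-occasion calcium model extends that approach; it cannot simply be copied.

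**A hidden rise is not shown.** It is tempting to infer that earlier discharge on vitamin D would mask a rise in calcium. The documents give no calcium SD, serial correlation, sampling rate or length-of-stay distribution. Under one set of assumptions the bias is negative and below one standard error; under another it is positive and large.

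**Conclusion.** The point holds as a recommended change to the SAP; the primary endpoint is not affected. Calcium is tested day by day without its universally required baseline, on a shrinking sample that is mostly clinically ordered except on day 0 for all and day 3 in the first 300.

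Two sizes can be given. The chance of at least one false-positive day is at most about 51%, and 14% to 49% over assumed correlations of 0.3 to 0.9. Baseline adjustment saves 9% to 36% of the variance for an assumed baseline correlation of 0.3 to 0.6. The selection bias could go either way and cannot be sized from the documents. The documents do not support reading the plan as one that would conceal a calcium rise, or as having no single test for hypercalcemia.

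**What to change.** In SAP 3.3.3, replace the daily t-tests with a repeated-measures model of serum calcium, days 0 to 14. It should have a common baseline mean in both arms, a treatment-by-day effect, all available values and a stated covariance structure, and be described as an extension of the SAP 3.3.2 approach.

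- Prespecify two main contrasts: day 3, and the average over days 1 to 14.
- Report the day-3 contrast also in the first 300, where sampling is mandated.
- Show the daily estimates with confidence intervals as description.
- Analyse ionized calcium separately. The protocol records serum or ionized values, whose exclusion limits (10.2 and 5.2 mg/dL) show different scales, and SAP 3.3.3 does not say which is tested.
- Keep the hypercalcemia chi-square, and state how many participants in each arm were measured.

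The cost is SAP wording, slightly more programming, and a covariance choice that must cope with sparse late data; no new data are needed. Two limits remain. The model handles discharge related to observed calcium, but not samples ordered for unobserved reasons. The 14-day average could dilute a transient rise, which is why day 3 stays as its own contrast.

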3.3.4 Baseline Characteristics

Summary statistics will be tabulated to show the distribution in each treatment group and in aggregate. Categorical variables will be summarized as frequency and percent and continuous outcomes as mean and standard deviation or median and interquartile range as appropriate. No p-values testing for a baseline difference between treatment groups will be presented

3.3.5 Figures

A log-rank test will be used to compare the time to 90 day mortality in the two treatment groups.

A quadratic smoothing spline in each treatment group will be used to display the relationship between the primary mortality outcome and baseline 25OHD level as measured by LCMS. Pointwise bootstrap confidence intervals for the difference between the two curves will be calculated at LCMS values of 5, 10, 15, 20, 25, and 30.

4. Supplementary Materials Outline and Statistical Methods

The supplementary materials will include the following tables and figures.

Table. Baseline Characteristics for confirmed not deficient (LCMS \geq 20), confirmed deficient, and screened deficient (all randomized)

- Demographics
- Co-Morbidities—Charlson, BMI, eGFR, pre-hospital level of care
- VIOLET Risk Factors
- Location—intent to admit, ICU destination
- Illness Severity—SOFA, LIPS, mechanical ventilation, ARDS, vasopressor use, vital signs, WBC, lactate
- Baseline vitamin D (home meds, vitD level, calcium level)

Table. Study Initiation/Dosing for confirmed deficient and screened deficient (all randomized)

- Inclusion to Randomization (time)
- Randomization to Drug Administration (time)
- Study Drug Dosing
- Study Drug Tolerance

Figure. Subgroup Analysis of Primary Endpoint (confirmed deficient)

- Age: <60, ≥60
- Sex: M, F
- Race/ethnicity: NH white, NH black, Hispanic, other
- Residence: independent, long-term care facility
- BMI: <20, 20-24.9, 25-29.9, 30-34.9, ≥35
- Pre-hospitalization vitamin D supplementation: none, 1-800 IU/day, >800 IU/day
- Baseline 25OHD level (by the LCMS): <12, 12-19, 20-29, ≥30 AND <10, 10-19, 20-29, ≥30 AND <20, ≥20
- Baseline renal function: eGFR 15 (or on dialysis), 15-29, 30-59, 60-89, ≥90
- ARDS risk factor: sepsis, pneumonia, shock, mechanical ventilation, other AND infectious, non-infectious
- LIPS score: <4, ≥4
- Pre-randomization mechanical ventilation status: Y, N
- Pre-randomization presence of ARDS: Y, N
- Source of ICU admission: ED, other
- ICU destination: MICU, other
- Modified intention to treat (received full study drug dose without vomiting within 1 hour): yes, no

Figure. Subgroup Analysis of Primary Endpoint for screened deficient (all randomized)

- Age: <60, ≥60
- Sex: M, F
- Race/ethnicity: NH white, NH black, Hispanic, other
- Residence: independent, long-term care facility
- BMI: <20, 20-24.9, 25-29.9, 30-34.9, ≥35
- Pre-hospitalization vitamin D supplementation: none, 1-800 IU/day, >800 IU/day
- Baseline 25OHD level (by the LCMS): <12, 12-19, 20-29, ≥30 AND <10, 10-19, 20-29, ≥30 AND <20, ≥20
- Baseline renal function: eGFR 15 (or on dialysis), 15-29, 30-59, 60-89, ≥90
- ARDS risk factor: sepsis, pneumonia, shock, mechanical ventilation, other AND infectious, non-infectious
- LIPS score: <4, ≥4
- Pre-randomization mechanical ventilation status: Y, N
- Pre-randomization presence of ARDS: Y, N
- Source of ICU admission: ED, other
- ICU destination: MICU, other
- Modified intention to treat (received full study drug dose without vomiting within 1 hour): yes, no

Figure. Time to Mortality to Day 90 for screened deficient (all randomized)

- Baseline LCMS <12
- Baseline LCMS 12 to <20
- Baseline LCMS ≥20

Table. Primary and Main Secondary Endpoints for screened deficient (all randomized)

Table. Adverse Events and Safety Outcomes for confirmed deficient, confirmed not deficient (LCMS \geq 20), and screened deficient (all randomized)

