### 5.2 Randomized Control Group

Participants randomized to the control group will receive a single liquid enteral dose of placebo that is matched to the vitamin D intervention to ensure blinding.

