2.6 Randomization and Study Initiation Time Window

All participants must be enrolled and randomized within 12 hours of meeting inclusion criteria. Study medication must be administered within 2 hours of randomization.

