2.11 Subgroups

The primary analysis will be based on randomized participants with baseline 25OHD levels <20 ng/mL by LC/MS/MS (confirmed vitamin D deficient cohort). Secondary analysis will be based on the screened vitamin D deficient cohort (all randomized patients). *A priori* subgroups for analysis will include age, sex, race/ethnicity, residence (independent vs. long-term care facility), BMI, pre-hospitalization vitamin D supplementation, baseline 25OHD level (by the LC/MS/MS method), baseline renal function, ARDS risk factor (e.g., infectious vs non-infectious), LIPS score, pre-randomization mechanical ventilation status, pre-randomization presence of ARDS, and source of ICU admission.

3. Main Manuscript and Statistical Methods

The primary analysis will be based on randomized participants with baseline 25OHD levels <20 ng/mL, as measured by LC/MS/MS (**confirmed vitamin D deficient cohort**). Additional analyses will be based on all randomized participants (**screened vitamin D deficient cohort**).

The main manuscript will include the following tables and figures.

Figure. CONSORT Diagram

Table. Baseline Characteristics (confirmed deficient cohort)

- Demographics
- Co-Morbidities—Charlson, BMI, eGFR, pre-hospital level of care
- VIOLET Risk Factors
- Location—intent to admit, ICU destination
- Illness Severity—SOFA, LIPS, mechanical ventilation, ARDS, vasopressor use, vital signs, WBC, lactate
- Baseline vitamin D (home meds, vitD level by LCMS, calcium level)

Figure. Change in LCMS from Day 0 to Day 3 for (screened deficient cohort)

Summary data in text of results or Supplementary Material

Table. Primary and Main Secondary Endpoints (confirmed deficient cohort)

Primary

- 90 day all-cause, all-location mortality

Secondary Clinical

- Hospital mortality to day 90
- Alive and home (prior level of care) at day 90
- All-cause, all-location 28 day mortality
- Hospital LOS
- Healthcare facility LOS
 - Include proportion that went to healthcare facility (vs home) separately
- VFD to day 28

- Include proportion ventilated to help with interpretation

Secondary Physiological

- Respiratory failure
 - New mechanical ventilation ever to day 7 (Y/N)
 - Lowest P/F in the first 7 days if on mechanical ventilation
- ARDS
 - New ARDS ever to day 7 (Y/N)
 - ARDS severity by Berlin definition at time of new ARDS diagnosis¹
 - Lowest P/F in the first 7 days if ARDS
- AKI to day 7
 - New RRT ever to day 7 (Y/N)

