4.2 Subgroup Analyses of Primary Endpoint

For the primary outcome, interactions between treatment groups and will be analyzed on the risk difference scale using a generalized linear model with a binomial distribution function and identity link function including a treatment effect, a sub-group effect, and a treatment by sub-group interaction.

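### Both supplementary subgroup figures contain a row defined by dosing and vomiting after randomisation, so randomisation protects neither level of that row nor its interaction test

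*SAP*

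**What the plan says.** SAP section 4 outlines two subgroup figures for 90-day mortality, one for the confirmed deficient cohort and one for all randomised participants. Each ends with the row "Modified intention to treat (received full study drug dose without vomiting within 1 hour): yes, no". It stands among baseline variables with no separate label or caveat.

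SAP 4.2 gives the method for subgroup analyses of the primary endpoint: a binomial model with identity link, "including a treatment effect, a sub-group effect, and a treatment by sub-group interaction". No row is exempted.

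On timing, SAP 2.6 states: "Study medication must be administered within 2 hours of randomization". Dose receipt, and any vomiting that follows, therefore come after allocation.

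The a priori subgroup lists in Protocol 3.7 and SAP 2.11 name baseline variables only, ending with "pre-randomization mechanical ventilation status, pre-randomization presence of ARDS, and source of ICU admission". Neither lists dose receipt or vomiting.

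Three places bear on the row's name. SAP 3.1 says "All analyses are intention to treat, that is, all randomized participants within each cohort (screened deficient, confirmed deficient) will be included". Protocol 7.1 uses modified intention to treat for confirmed deficient participants who received either product, with no condition on a full dose or on vomiting. SAP section 4 attaches the same term to a full dose without vomiting.

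The dosing table planned in SAP section 4 already has a line for "Study Drug Tolerance".

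**The concern.** A subgroup comparison keeps the protection of randomisation only when assignment cannot influence who is in the subgroup. Age and sex meet that condition. Keeping down a full dose for an hour need not: vomiting, or stopping part-way through the dose, may depend on the product swallowed, and it may also mark sicker patients. If the arms differ in tolerance, the *yes* patients in one arm are not the counterparts of the *yes* patients in the other, and likewise for *no*. An interaction test between the two rows then tests case mix as well as effect modification.

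The SAP deals with this kind of selection elsewhere. SAP 3.1 carries a case-mix caveat for outcomes defined only in patients on study, and SAP 3.3.1 and 3.3.3 use survivor average causal effect methods for survivor-only outcomes. This row gets neither.

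What is at stake is how a supplementary figure is read. Some readers will take the *yes* row as the effect in patients who really got the drug, and the label may lead them to take it for the modified intention-to-treat population of Protocol 7.1.

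**Working it through.** **Stated figure.** The plan gives no number on this point. The only related one is the 87.4% power in Protocol 2.10 and 7.1, used here just to fix the sample size: 80% of 3000 = 2400, or 1200 per arm at 1:1. With 20% against 15% and one-sided 0.025, a fixed design gives 89.7%. The three looks under the 0.025t^4 spending function give 89.4%, and adding an assumed futility stop at 5% predictive probability gives 87.7%. That is consistent with the stated power.

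**Who is in the *no* row.**
- Never dosed: settled before exposure and under blinding.
- Partly dosed: already exposed, and stopping may reflect intolerance.
- Vomited within 1 hour: after exposure.

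Only the first group is clearly free of any effect of the product.

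**Illustration 1: the *no* row larger on vitamin D.** All rates are assumptions. Overall mortality is 20% in both arms, and the drug changes no patient's death.
- Share in *no*: vC = 5% on control, vT = 10% on vitamin D.
- Control *no*-row mortality: m = 30% or 40%.
- Control *yes*-row mortality: (0.20 - vC·m)/(1 - vC) = 0.185/0.95 = 19.5%, or 0.180/0.95 = 18.9%.
- The extra vitamin D *no* patients, share e = vT - vC = 5%, have mortality s.
- Vitamin D *no* row: (vC·m + e·s)/vT.
- Vitamin D *yes* row: (0.20 - vC·m - e·s)/(1 - vT).

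Example with m = 40%, s = 10%: *no* row (0.020 + 0.005)/0.10 = 25.0%, a difference of -15.0 points. *Yes* row (0.180 - 0.005)/0.90 = 19.4%, a difference of +0.5. The *no* row has 60 and 120 patients and the *yes* row 1140 and 1080. The interaction is -15.5 points with standard error 7.6, so a two-sided 5% test rejects in 53% of trials.

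| Mortality of the extra *no* patients | *No* row, points (m = 30%, 40%) | *Yes* row, points | Interaction rejects |
|---|---|---|---|
| As ordinary *yes* patients (about 19%) | -5.3, -10.5 | 0, 0 | 11%, 27% |
| 10% | -10.0, -15.0 | +0.5, +0.5 | 31%, 53% |
| As other *no* patients (m) | 0, 0 | -0.6, -1.2 | 5%, 5% |

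If the arm does not affect membership (5% in each arm, same case mix), both rows show 0 and the test rejects at its nominal 5%. If the excess were on placebo, the signs would reverse. A wider gap moves everything further: at 5% against 15%, the *yes* row spans +1.1 to -2.5 points and the *no* row 0 to -20.

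**Illustration 2: small vomiting rates, *yes* row only.** Assume 17.5% mortality in both arms, the mean of 20% and 15%, and mortality m among vomiters in both arms. Non-vomiter mortality is (0.175 - v·m)/(1 - v).
- v = 3% against 1%: -0.26 points (m = 30%), -0.47 points (m = 40%).
- v = 5% against 2%: -0.40 and -0.73 points.

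The standard error of the risk difference at 1200 per arm is √(2 × 0.175 × 0.825/1200) = 1.55 points, so these shifts are 0.17 to 0.47 standard errors. The two-sided 5% error rate rises to between 5.3% and 7.5%.

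**The case against.** The strongest reply is that bias is possible but not shown. The placebo is "matched to the vitamin D intervention to ensure blinding" (Protocol 5.2), and Protocol 3.3 and 5.1 report no vitamin D-related adverse events at this dose. The gastrointestinal mechanism in Protocol 9.1 is hypercalcaemia, while Protocol 3.6.2.3 puts the 25OHD peak at day 3, not within an hour. No passage gives a vomiting rate or suggests that it differs by arm. This stands, and it limits the point to unprotected comparisons rather than demonstrated bias.

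A reader might infer that the *yes* row leans towards benefit and could make a negative trial look positive in treated patients. The documents do not support that. The false benefit in Illustration 2 requires the extra vomiters to be sicker than average. If the product itself made them vomit, they could be ordinary patients, in which case the *yes* row barely moves, or healthier ones, in which case it moves the other way. Even the assumed shifts are under half a standard error.

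It can also be said that these are supplementary figures, that the row prints its own definition, and that SAP 4.2 names no individual row. The first two are true and keep the stakes low. On the third, SAP 4.2 is the only method given for subgroup analyses of the primary endpoint, and this row sits in the figures so titled, so the natural reading includes it.

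**Conclusion.** The point holds as a defect of classification and labelling in the supplement. A variable settled after randomisation, and partly after exposure, is treated as a baseline subgroup and given an interaction test. It is also missing from the a priori lists, and its name has another meaning in Protocol 7.1.

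Any distortion requires that the arm affects dosing or tolerance. If so, it falls mainly on the small *no* row and on the interaction, and it can go in either direction. With an assumed 5% against 10% in the *no* row, the *yes* row moves by no more than about 1.2 points, against a design difference of 5. The sizes rest wholly on assumed rates of non-receipt, vomiting and mortality. The primary intention-to-treat analysis is not touched.

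**What to change.** - Delete the row from both subgroup figures in SAP section 4 and exclude it from the interaction analysis in SAP 4.2.
- Report incomplete dosing and vomiting within 1 hour by arm, as outcomes, under the dosing and tolerance lines already planned in the study initiation and dosing table.
- Add a supplementary sensitivity estimate of the primary endpoint in participants given any study drug, which is the modified intention-to-treat set of Protocol 7.1. That status is settled under blinding and before exposure.
- If an estimate in participants who kept down the full dose is still wanted, show it outside the subgroup figures, labelled as a non-randomised comparison and without an interaction p-value.
- Reconcile modified intention to treat across Protocol 7.1, SAP 3.1 and SAP section 4, so that the term has one meaning.

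The cost is SAP wording and one supplementary figure row. No new data are needed.
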